MultiPoint™ pacing (MPP) is a new pacing feature in the Quadripolar CRT-D system that allows sequential pacing of the LV with two pacing vectors compared to one vector in a traditional CRT-D system. A combination of any two of the 10 available vectors with inter-stimulus delays can be used. MPP via one LV lead may have the potential to act as an alternative to non-invasively optimize LV lead placement, and it may improve hemodynamics and the response to CRT. Studies showed that simultaneously exciting a larger mass or volume of cardiac tissue results in faster depolarization velocity and shorter left ventricular trans-ventricular conduction times²³⁻²⁴. In addition, by capturing a larger volume of cardiac muscle, the site of latest intrinsic activation within the left ventricle may be more likely to be depolarized early, resulting in better synchronization and maximizing cardiac output.

Since MPP delivers two pulses at programmable delays (LV1 and LV2) to two LV sites, the initial volume of excited cardiac tissue is increased. By capturing more mass at the site of initial depolarization there is a greater likelihood of pacing the site of latest systolic delay. Both of these methods have been shown to improve LV function²⁵⁻²⁶ and it is believed that this additional improvement in LV function may benefit those patients who are otherwise identified as non-responders to conventional BiV pacing.

3 Investigational Design

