Informed Consent Procedure and Inclusion/Exclusion Criteria check:

Patient's eligibility criteria and Informed consent Procedure is performed before any study related activity. Please refer to section 4.2.1 "Enrollment visit" for further details.

Implant Procedure Details:

Implant Procedure details (standard CRT implant) will be collected at Implant visit. Indicate model n°, serial n° and date of implant of entire implanted system (CRT device, RA lead, RV lead and LV lead), even in case of implant failure. Final positions of all the implanted leads must be specified: right atrium, right ventricle and left ventricle lead positions.

Fluoroscopy Images Collection (EDC upload):

As the lead placement is important to understanding the subject's response to CRT, two anonymized Fluoroscopy images are requested to be collected:

- LAO (Left Anterior Oblique, $45^{\circ}\pm 10^{\circ}$)
- RAO (Right Anterior Oblique, $45^{\circ}\pm 10^{\circ}$).

The position of all leads must be clearly visible to allow matching with the venous anatomy. These anonymized images should be uploaded to the EDC system using the feature "Attachments to CRFs", for further details on this topic please refer to Appendix E "Guidelines" part 1.1.

Implant Procedure Success Confirmation:

In the Patient Classification visit, the confirmation of a successful implant procedure will be asked in order to classify the subject as Qualified Subject or not.

MPP Vector Test:

In order to allow future activation of MPP, specific LV pacing capture thresholds and Phrenic Nerve Stimulation (PNS) tests must be performed for the 4 cathodes during the Patient Classification visit.

The test is considered positive in case is possible to identify at least 2 vectors from different Groups (with different Cathodes) free from Phrenic Nerve Stimulation (PNS) and with a Pacing Threshold that do not exceed 4.5V at 0.5ms pulse duration in CRT-D devices and at 0.4ms pulse duration in CRT-P devices.

Please refer to Appendix E "Guidelines" part 6 for the detailed testing procedure.

Subject Data and Medical History:

Subject's Year of Birth and Gender will be collected at the Baseline visit together with cardiomyopathy etiology and co-morbidities.

Current Cardiac Medications/Changes in Cardiac Medications:

The current cardiac medications will be collected at Baseline, while during the Follow-up Visits only the changes will be documented.

Patient Global Assessment:

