5.1 Statements of Compliance

The investigation will be performed in accordance with the most current versions of the World Medical Association (WMA) Declaration of Helsinki and any regional and/or national regulations as appropriate.

ISO14155 shall be used as a guideline with following exceptions:

- Limited AE reporting → refer to section “5.3.2 Procedure for assessing, recording and reporting adverse events, adverse device effects, serious adverse events and serious adverse device effects”
- Device Deficiencies as this is a post-market study
- Device Accountability

The investigator shall not start enrolling patients or requesting informed consent prior to obtaining Ethics Committee approval and Competent Authority approval, if applicable, and authorization from the sponsor in writing for the investigation.

In case additional requirements will be imposed by the Ethics Committee or Competent Authority they shall be followed, if appropriate.

As sponsor, SJM has taken up general liability insurance in accordance with the requirements of the applicable local laws.

If required, additional subject coverage or an investigation specific insurance shall be provided by the Sponsor as well.

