5.3.1.4 Adverse Device Effect (ADE)

An adverse event related to the use of a medical device

This definition includes adverse events resulting from insufficient or inadequate instructions for use, deployment, implantation, installation, or operation, or any malfunction of the medical device.

This definition includes any event resulting from the use error or from intentional misuse of the medical device.

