5.3.1.5 Serious Adverse Device Effect (SADE)

Adverse device effect that has resulted in any of the consequences characteristic of a serious adverse event

5.3.2 Procedure for assessing, recording and reporting adverse events, adverse device effects, serious adverse events and serious adverse device effects:

Safety surveillance and reporting will be done for all subjects enrolled in this investigation.

Safety surveillance within this investigation and the safety reporting both performed by the investigator, starts as soon as the subject is enrolled in this investigation (date of signature of the informed consent form). The safety surveillance and the safety reporting will continue until the last investigational visit has been performed or the subject is deceased or the subject/investigator concludes his participation into the investigation.

Adverse Events Reporting

The investigator must report all SAEs and SADEs to the Sponsor as soon as possible but no later than outlined below.

Clinical Site	Reporting timelines
All Sites	SAEs or SADEs must be reported no later than 3 calendar days from the day the site personnel became aware of the event or as per the investigative site's local requirements, if the requirement is more stringent than those outlined.

The date the site staff became aware the event met the criteria of an SAE or SADE must be recorded in the source document.

The Investigator will further report the SAE or SADE to the local EC according to the institution's EC reporting requirements and in accordance with national and local laws and regulations.

Adverse events (including Adverse Device Effects) that are not serious will be reported to the Sponsor, as soon as possible after the occurrence of the event.

Non-Serious Adverse Events documentation and reporting are limited to cardiovascular events. Within cardiovascular, all arrhythmias that require medical assessment and/or intervention should be documented as serious adverse event.

All HF hospitalization \geq 24 hours are to be documented and reported to the sponsor according to the reporting requirements for all SAEs and SADEs (Refer to Adverse Events Reporting section).

All HF hospitalization $<$ 24 hours requiring administration of IV inotropes or diuretics are to be documented and reported to the sponsor according to the reporting requirements for all SAEs and SADEs (Refer to Adverse Events Reporting section).

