6.2.2 Associated with device or leads implant procedure

Possible adverse events (in alphabetical order) associated with the implantation of pacing system (CRT device and leads) include but are not limited to:

- Acute hemorrhage/bleeding
- Air emboli
- Allergic reaction to contrast media
- Arrhythmia acceleration
- Body rejection phenomena
- Cardiac or venous perforation
- Cardiac tamponade

- Cardiogenic shock
- Chronic nerve damage
- Cardiac/coronary sinus dissection
- Cardiac/coronary sinus perforation
- Coronary sinus or cardiac vein thrombosis
- Death
- Excessive bleeding
- Extracardiac stimulation (phrenic nerve, diaphragm, chest wall)
- Fluid accumulation
- Hematoma/seroma formation
- Hemothorax
- Induced atrial or ventricular arrhythmias
- Infection
- Lead migration, dislodgment or poor lead placement
- Myocardial irritability
- Myocardial damage
- Myopotential sensing
- Pericardial effusion
- Pericardial rub
- Pneumothorax
- Prolonged exposure to fluoroscopic radiation
- Pulmonary edema
- Renal failure from contrast media used to visualize coronary veins
- Rise in threshold and exit block
- Thromboemboli
- Valve damage
- Venous occlusion

These events are not unique to study procedures and could occur during any device implant outside of the study.

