 - b. Read the first question to the patient - "Did your heart failure prevent you from living as you wanted during the last month by causing swelling, for example, in your ankles, legs"? Tell the patient, "If you did not have any ankle or leg swelling during the last month you should circle nought after this question to indicate that swelling was not a problem during the last month". Explain to the patient that if he or she did have swelling that was caused by a sprained ankle, or some other cause that was definitely not related to heart failure, he or she should also circle nought. Tell the patient, "If you are not sure why you had the swelling or think it was related to your heart condition, then rate how much the swelling prevented you from doing things you wanted to do and from feeling the way you would like to feel". In other words, how bothersome was the swelling? Show the patient how to use the 1 to 5 scale to indicate how much the swelling affected his or her life during the last month - from very little to very much.
4. Let the patient read and respond to the other questions. The entire questionnaire may be read directly to the patient, being careful not to influence responses by verbal or physical cues.
5. Check to make sure the patient has responded to each question and that there is only one answer clearly marked for each question. If a patient elects not to answer a specific question(s) indicate so on the questionnaire.
6. Score the questionnaire by adding the responses to all 21 questions. In addition, physical (items 2, 3, 4, 5, 6, 7, 12 and 13) and emotional (items 17, 18, 19, 20, and 21) dimensions of the questionnaire have been identified by factor analysis, and may be examined to further characterize the effect of heart failure on a patient's life.

These questions concern how your heart failure (heart condition) has prevented you from living as you wanted during the last month. The items listed below describe different ways some people are affected. If you are sure an item does not apply to you or is not related to your heart failure, then circle 0 (No) and go on to the next item. If an item does apply to you, then circle the number relating to how much it prevented you from living as you wanted.

Part 6: MultiPoint Pacing Vectors Test

This appendix describes the test procedure (Vector Test) that needs to be performed in order to establish if the MPP feature can be turned ON. The feature will be tested at the Classification visit.

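### Section 5.3.2 leaves unclear whether non-serious, non-cardiovascular device effects such as phrenic nerve stimulation are recorded, so any excess with MPP ON could be missed or understated

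*Combined protocol and SAP*

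**What the plan says.** The reporting rule is in protocol section 5.3.2. On non-serious events it first states: "Adverse events (including Adverse Device Effects) that are not serious will be reported to the Sponsor". That sentence carries no cardiovascular limit. The next paragraph states: "Non-Serious Adverse Events documentation and reporting are limited to cardiovascular events". Section 5.1 declares "Limited AE reporting" as an exception to ISO 14155 and points to 5.3.2. It also lists device deficiencies as an exception. Section 5.3.1.4 defines an adverse device effect as "An adverse event related to the use of a medical device".

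Section 6.2.2 includes "Extracardiac stimulation (phrenic nerve, diaphragm, chest wall" among the anticipated events, under the implant procedure. Section 6.1 describes the additional risk of MPP as minimal and names pro-arrhythmia as the theoretical concern. Section 2 explains that "MPP delivers two pulses at programmable delays (LV1 and LV2) to two LV sites".

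Before a subject qualifies, the MPP Vector Test (section 4.2) requires at least two vectors with different cathodes that are "free from Phrenic Nerve Stimulation (PNS) and with a Pacing Threshold that do not exceed 4.5V". Appendix E Part 6 gives the timing: "The feature will be tested at the Classification visit". Table 2 adds a check at 6 months, in Phase II only and before randomization.

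SAP 6.3 summarises adverse events, serious adverse events and unanticipated adverse device effects as counts, percentages of subjects and rates per patient-year. Unlike SAP 6.1 and 6.2, it does not say that the summary is by treatment group.

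**The concern.** The two sentences give sites different instructions for one class of event: non-serious, related to the device, and not cardiovascular. Stimulation of the phrenic nerve or diaphragm by left ventricular pacing is the clearest member of that class. The protocol treats it as important enough to be one of the two criteria of the vector test, the other being capture threshold. MPP paces a second left ventricular site, so a difference between arms is plausible.

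If such events are not entered as adverse events, they cannot appear in the SAP 6.3 summary. The trial could then neither support nor contradict the section 6.1 statement of minimal added risk as far as non-serious stimulation is concerned. With up to 250 centers, it is likely that the two sentences will be read in different ways.

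**Working it through.** The plan states no figure on this point, so there is nothing to reproduce. The check sets the passages side by side and then uses simple algebra for the direction of any error.

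**1. Does the limit reach adverse device effects?** By 5.3.1.4 every adverse device effect is an adverse event. A limit on non-serious adverse events therefore covers non-serious adverse device effects unless the text exempts them, and no text does. The sentence before the limit names them as reportable. Two readings are open:

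| Reading | Non-serious phrenic nerve stimulation |
|---|---|
| First sentence governs device effects | Recorded |
| Second sentence restricts the first | Not recorded |

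**2. Do scheduled assessments fill the gap?** Inputs from section 4.2: classification at 0 to 7 days after implant; 6-month visit at 183 ± 14 days, that is 169 to 197; 12-month visit at 365 ± 21 days, that is 344 to 386.

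- Vector test to the 6-month visit, where MPP is switched on: from 169 − 7 = 162 days to 197 − 0 = 197 days. Section 6.2.2 lists lead migration as an anticipated event.
- The 6-month check is limited to Phase II and precedes randomization. No such check is shown for Phase I.
- 6-month to 12-month visit: from 344 − 197 = 147 days to 386 − 169 = 217 days. Table 2 shows no vector test at 12 months, and section 4.2 describes the device test there as sensing, pacing and impedance measurements.

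**3. Which other records could show an event?** Stimulation that meets a seriousness criterion is reported as serious. The System Revision form is available from implant onward. Device sessions are uploaded at 6 and 12 months. Section 4.2.7 requires changes to MPP programming at unscheduled visits to be documented, but asks for no reason, so a switch-off because of stimulation need not be distinguishable from any other. None of these records is itself an entry in the adverse event summary unless the event is serious.

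**4. Direction and size.** Let p_ON and p_OFF be the true risks of non-serious stimulation and c the share recorded, taken as equal in the two arms. Then:

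recorded difference = c × (p_ON − p_OFF)

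The documents give neither risk. With p_ON = 4% and p_OFF = 2%, chosen only for illustration:

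| c | Recorded ON | Recorded OFF | Difference | Ratio |
|---|---|---|---|---|
| 0 | 0% | 0% | 0 points | undefined |
| 0.5 | 2% | 1% | 1 point | 2 |
| 1 | 4% | 2% | 2 points | 2 |

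If p_ON = p_OFF, the recorded difference is 0 for every c.

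Randomization is stratified by center (section 3.8), so one center's reading of the rule falls on both its arms. That supports an equal c but does not guarantee it.

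**The case against.** The strongest reply is that narrow collection of non-serious events is a declared choice. Section 5.1 names it as an exception, and the devices are approved and market-released. This stands as a reason for a limit, but it does not settle whether the limit covers device effects, on which 5.3.2 says two things.

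A reader might infer that non-serious stimulation is not captured at all. The documents do not support that. One of the two sentences calls for it to be reported, and the heading of 5.3.2 names adverse device effects separately from adverse events, so a site could reasonably go on reporting them. Reprogramming and system revisions are documented. The blank case report forms and Appendix E Part 7 are not in the available text, so a question on stimulation there cannot be ruled out.

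A reader might also infer that MPP will look safer than it is. That is not shown either:

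- The rule is the same in both arms.
- No rate is given for either arm.
- Subjects without two stimulation-free vectors do not qualify, which may leave no excess.
- Extracardiac stimulation is listed under the implant procedure and not as an effect of MPP.
- With equal partial recording the risk ratio is unchanged and only the absolute difference shrinks.
- SAP 6.3 is descriptive and states no test.

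All of these points stand. They limit the claim to what could be missed; they do not remove the conflict between the sentences.

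**Conclusion.** The point holds as a conflict in the safety-reporting rule with a possible effect on the safety summary. Under one of the two readings, non-serious, non-cardiovascular device effects go unrecorded, and the documents available schedule no assessment of phrenic nerve stimulation once MPP is on. If a true excess with MPP ON exists, its recorded absolute size lies between zero and the true value, given equal recording in the two arms. Whether there is an excess cannot be judged from the documents, so a bias in favour of MPP remains a possibility only. The size cannot be estimated; the 4% and 2% in the working are assumptions that show the mechanism and should not be read as expected rates. The primary endpoint is not touched. The correction is worth making because it is cheap and concerns the feature under test.

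**What to change.** 1. In section 5.3.2, reconcile the two sentences so that the cardiovascular limit applies only to non-serious events unrelated to the device or the procedure. State that all adverse device effects, serious or not, are recorded in both arms, and name extracardiac stimulation as an example. Amend the exception in section 5.1 to match.
2. Require a reason for any MPP reprogramming or switch-off at the 12-month visit and at unscheduled visits. If the follow-up form does not already have one, add an item on extracardiac stimulation for both arms.
3. In SAP 6.3, state that adverse device effects and MPP switch-offs with their reasons are summarised by treatment group.

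The cost is a modest number of extra non-serious event forms, one or two form fields, and a narrower ISO 14155 exception. Events in subjects already followed under the present wording cannot be recovered in a uniform way, so the summary should separate events collected before and after the change.

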5.3.1.3 Serious Adverse Event (SAE)

An adverse event that led to:

- Death
- A serious deterioration in the health of the subject, that either resulted in:

- A life-threatening illness or injury OR
- A permanent impairment to a body structure or a body function OR
- An in-patient or prolonged hospitalization OR
- A medical or surgical intervention to prevent life-threatening illness or injury or permanent impairment to a body structure or a body OR
- A malignant tumor
- Fetal distress, fetal death or a congenital abnormality or birth defect

A planned hospitalization for a pre-existing condition, or a procedure required by the CIP is not considered a serious adverse event.

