6.1 Risks

The risks associated with the use of the Quadripolar CRT device system are anticipated to be comparable to those associated with the use of other currently available CRT devices, and leads. Patients participating in this study are indicated for a CRT system as part of their standard medical management and are subject to the risks associated with these devices (refer to Section 6).

Additional risks associated with MPP compared to conventional BiV pacing are considered to be minimal. There is a theoretical risk that addition of a second LV pacing pulse could have a pro-arrhythmic effect. However, among both preclinical and clinical experience, no arrhythmias have been reported that have been caused by MPP. The risk of reentrant conduction pathways and induced VT is similar to that caused by standard BiV pacing.

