6.3 Adverse Events

Adverse events, serious adverse events and unanticipated adverse device effects (UADE) will be summarized in terms of number of events, the percentage of subjects with events, and event rate estimated as # event/patient-years.

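### Protocol 5.3.2 has arrhythmias that need only medical assessment documented as SAEs, in conflict with 5.3.1.3, so the SAE count alone cannot show whether MPP changes the rate of serious arrhythmia

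*Combined protocol and SAP*

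**What the plan says.** **Definition.** Protocol 5.3.1.3 makes an event serious if it led to death, to a fetal outcome, or to "A serious deterioration in the health of the subject, that either resulted in" one of a listed set of consequences. An intervention counts only in this form: "A medical or surgical intervention to prevent life-threatening illness or injury or permanent impairment to a body structure or a body OR". Needing medical assessment is not on the list. A serious adverse device effect (5.3.1.5) takes over the same consequences: "Adverse device effect that has resulted in any of the consequences characteristic of a serious adverse event".

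**Reporting rule.** Protocol 5.3.2 first narrows collection: "Non-Serious Adverse Events documentation and reporting are limited to cardiovascular events". It then adds: "Within cardiovascular, all arrhythmias that require medical assessment and/or intervention should be documented as serious adverse event". SAEs go to the sponsor within 3 calendar days and on to the local ethics committee. Reporting starts at consent.

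**Risk.** Protocol 6.1 calls the extra risk of MPP minimal and names one mechanism: "There is a theoretical risk that addition of a second LV pacing pulse could have a pro-arrhythmic effect".

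**Analysis.** SAP 6.3 says: "Adverse events, serious adverse events and unanticipated adverse device effects (UADE) will be summarized in terms of number of events", together with the percentage of subjects affected and a rate per patient-years. It gives no event type, treatment arm or start point. SAP 6.2, on mortality, gives both arm and day 0 (randomization).

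**The concern.** Sections 5.3.1.3 and 5.3.2 give different answers for the same event. An arrhythmia that was assessed, had no listed consequence and needed no preventive intervention is not an SAE under the definition. Under the reporting rule it is documented as one.

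The stake is how the safety results can be read. If sites follow the plan as written, the SAE category contains events that fail the trial's own definition of serious. The overall SAE rate is then higher than the definition would give. The category also no longer separates serious arrhythmia from arrhythmia that was looked at and left alone, and arrhythmia is where the protocol itself places the added risk of MPP. The trigger is also a judgement: the text does not say when an arrhythmia requires assessment, and no blinding of the centre that programs MPP ON or OFF is described.

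**Working it through.** **1. The two rules side by side**

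| Arrhythmia | 5.3.1.3 | 5.3.2 |
|---|---|---|
| Death, life threat, permanent impairment or hospitalization | SAE | SAE |
| Intervention to prevent life threat or permanent impairment | SAE | SAE |
| Other intervention, no listed consequence | not an SAE | SAE |
| Medical assessment only | not an SAE | SAE |

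The last two rows conflict. No text presents 5.3.2 as a deliberate extension of the definition.

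**2. Is 5.3.2 only a faster reporting route?** The wording points the other way. The neighbouring sentences on heart failure hospitalization have those events reported under the SAE requirements, which borrows the route. The arrhythmia sentence has the event documented as an SAE. Section 5.3.2 also asks for the date on which staff learned that the event met the SAE criteria. For an assessed-only arrhythmia, no such date exists under 5.3.1.3.

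**3. What mixing does to an arm comparison**

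The plan states no arrhythmia rate, SAE rate or safety power, so there is no figure to reproduce. All inputs here are assumptions:
- arrhythmia meeting 5.3.1.3: 2% OFF, 4% ON;
- assessed-only arrhythmia in further subjects: *a* = 2%, 5% or 10% in OFF;
- n = 250, 500 or 1000 per arm, 1:1, two-sided alpha 0.05.

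The sample-size inputs are redacted. For orientation, protocol 3.5 gives 5638 qualified subjects. The background section quotes non-response from 20% to 50%, so both phases together would give 5638 × 0.20 / 2 = 564 to 5638 × 0.50 / 2 = 1410 per arm, before exclusions. (Section 3.10.2 gives 5914 qualified subjects.)

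Power = Φ[(d − 1.96·SE0)/SE1], where d is the difference in proportions, SE0 = √(2·p̄(1−p̄)/n) and SE1 = √((p_ON(1−p_ON) + p_OFF(1−p_OFF))/n).

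Example, n = 500:
- Definition only, 4% against 2%: SE0 = √(0.03 × 0.97 × 2/500) = 0.01079; SE1 = √((0.0384 + 0.0196)/500) = 0.01077; (0.02 − 0.02115)/0.01077 = −0.106; power 46%.
- With *a* = 5% in both arms, 9% against 7%: SE0 = 0.01716; SE1 = 0.01715; (0.02 − 0.03363)/0.01715 = −0.795; power 21%.

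*Case A: assessed-only arrhythmia equally common in both arms.* Risk ratio = (4% + a)/(2% + a).

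| *a* | ON vs OFF | Risk ratio | Power, n = 250 | n = 500 | n = 1000 |
|---|---|---|---|---|---|
| none (5.3.1.3 only) | 4% vs 2% | 2.00 | 26% | 46% | 75% |
| 2% | 6% vs 4% | 1.50 | 18% | 31% | 54% |
| 5% | 9% vs 7% | 1.29 | 13% | 21% | 38% |
| 10% | 14% vs 12% | 1.17 | 10% | 15% | 26% |

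*Case B: MPP doubles assessed-only arrhythmia as well.* The rates become 8% vs 4%, 14% vs 7% and 24% vs 12%. At n = 500, power is 76%, 95% and above 99%, against 46% under the definition. The gap is then 4, 7 or 12 points, of which only 2 are serious arrhythmia.

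*Case C: MPP has no effect on serious arrhythmia (2% in both arms) but doubles assessed-only episodes from 5% to 10%.* The SAE data show 2% + 10% = 12% against 2% + 5% = 7%, a risk ratio of 1.71 with no difference in serious arrhythmia.

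The same rule can therefore dilute a real difference, enlarge it, or produce an SAE difference made up of non-serious events. The count alone cannot tell these apart.

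**The case against.** **Nothing is lost.** The rule over-includes arrhythmias and drops none, and it applies to both randomized arms. A reader might infer that the SAE table hides pro-arrhythmia or cannot show it at all. The documents do not support that: an arm comparison of all assessed or treated arrhythmias remains possible, and Case B shows it could be more sensitive. This objection stands. What is lost is the severity split.

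**SAP 6.3 is the larger obstacle.** It names no event type, arm or post-randomization period, so a pooled SAE count would not show pro-arrhythmia even if 5.3.2 matched the definition. This also stands. Correcting 5.3.2 alone would not be enough.

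**The rule may be a deliberate, conservative capture rule applied uniformly.** This is possible. A reader might infer that the same event will be serious at one center and non-serious at another, but nothing shows that some sites would disregard a specific instruction that all must follow. The contradiction in the text remains either way.

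**Requiring assessment is narrower than being reviewed.** Device diagnostics are downloaded at every in-clinic follow-up. A brief episode seen there did not necessarily require assessment, so a flood of trivial SAEs should not be assumed. This stands, and it is why the size of the background is left open.

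**The form may already record the criterion.** The fields of the adverse event form are not in the supplied text. If it has a seriousness-criterion field, the split is recoverable and only the text and tables need work.

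**Safety is not a listed endpoint.** This is true, and no efficacy analysis is affected.

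**Conclusion.** The conflict between 5.3.1.3 and 5.3.2 is established from the text. If 5.3.2 is followed, the SAE figures in SAP 6.3 include arrhythmias that do not meet the trial's definition. Overall SAE rates are inflated by an unknown amount, and the SAE count by itself does not show whether MPP changes the rate of serious arrhythmia.

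Neither the size nor the direction of any distortion can be fixed from the documents. The figures above illustrate a range and rest on assumed event rates and arm sizes. In particular, the fall in the risk ratio from 2.0 to between 1.50 and 1.17 requires that MPP leaves assessed-only arrhythmia unchanged. A reader might take that fall as the expected effect, but the documents give no basis for preferring it to the cases in which the mixing exaggerates a difference.

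This affects the interpretability of the safety report. It does not affect the primary endpoint. It is worth correcting because it touches the one MPP-specific risk that the protocol names and the correction is cheap.

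**What to change.** 1. **Protocol.** Reconcile 5.3.1.3 and 5.3.2. Keep the capture of these arrhythmias, the 3-day timeline and any ethics committee reporting that is required. Record for each arrhythmia which 5.3.1.3 criterion it met, or that it met none.
2. **SAP 6.3.** Tabulate arrhythmia events by treatment arm, counted from randomization as day 0 (as SAP 6.2 does for mortality), separately for those that meet and do not meet 5.3.1.3.
3. **Supportive table.** Summarize by arm the device-recorded VT/VF episodes and delivered therapies between the 6- and 12-month session uploads, which the protocol already requires. Show CRT-D and CRT-P separately. Note that detection depends on device programming, which is left to the investigator apart from MPP, so this table is not fully independent of site practice.

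**Cost.** A wording change in the protocol and a small amount of extra tabulation. Arrhythmia SAEs already entered need their seriousness criterion checked, unless the adverse event form already records it. No new visit or measurement is needed.
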